If a patient does not meet the requirements for treatment continuation on any day other than D1 (D2-10 or D15-24) of any cycle, treatment will be immediately interrupted and the corresponding Debio 1143 dose (and nivolumab if on D15) will be omitted. Patients should be re-assessed, ideally, every 48-72 hours, if clinically indicated, and treatment will only be resumed after all re-treatment criteria are met. On D1, treatment can be delayed more than 3 days if required; in this case, the assessment schedule will shift accordingly, and all assessments planned for D1 will be performed on the day treatment is re-started. However, if treatment is interrupted during any day other than D1 and the re-treatment criteria are not met within 72 hours, treatment will be resumed only on D1 of the next cycle.

A maximum delay of 4 and 8 weeks (+1-week tolerance) for Debio 1143 and nivolumab, respectively, is allowed. After this delay-period, treatment will be withdrawn. Patients withdrawing from treatment for any reason will be followed for safety up to 5 months (±15 days) after the last nivolumab infusion, complete resolution or stabilization of any ongoing toxicity, unless the patient starts a new treatment, end-of-life-care or withdraws consent.

Patients experiencing immune-related AEs, that require withholding nivolumab infusions temporarily until resolution to at least Grade 1, may withhold nivolumab for a maximal period of up to 8 weeks (±1 week

tolerance). During this period, patients may continue to receive Debio 1143 as per protocol, if appropriate. Patients requiring more than 8 weeks ( $\pm 1$  week) of nivolumab interruption and those who permanently discontinue nivolumab for any reason, will discontinue Debio 1143 permanently and will be withdrawn from the study. The nivolumab dose will not be adjusted under any circumstances.

Patients experiencing any treatment-related grade 4 toxicity (clinically or laboratory, excluding grade 4 amylases and/or lipase and/or non-febrile neutropenia) will withdraw from treatment definitively without further reduction (see [section 8.3.2.1](#) for details).

Patients experiencing any other treatment-related toxicity fulfilling applicable DLT criteria (as shown below) at any time during the study must stop treatment and may only resume treatment after adequate recovery to re-treatment criteria.

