Treatment must be re-started with a Debio 1143 dose reduction. Individual patients may have up to two dose adjustments of 50 mg/d (each one) up to a minimum dose of 100 mg/d Debio 1143 (i.e. 1st dose reduction 150 mg/d, 2nd dose reduction 100 mg/day). Patients still requiring a dose adjustment with a dose of 100 mg/d will be withdrawn from the study. Once adjusted, Debio 1143 dose will not be re-escalated under any circumstances.

Up to 2 dose reductions must be implemented in the event of any of the following:

- Any Debio 1143-related Grade 4 hematologic toxicity
- Debio 1143-related febrile neutropenia any grade, or Grade 3 thrombocytopenia if associated with bleeding or requiring platelet transfusion
- Debio 1143-related grade 2 or higher alanine transaminase (ALT)/ aspartate transaminase (AST) increase with a concurrent increase of total bilirubin  $\geq 2$  x upper limit of normal (ULN) and concurrent with alkaline phosphatase (ALP)  $\leq 2$  x ULN (Hy's law), in the absence of objective causes of biliary obstruction due to obvious disease-related causes
- Any Grade 3, treatment-related, non-hematologic clinical toxicity lasting 3 or more days despite optimal supportive care, or requiring admission for appropriate medical management; hypersensitivity and/or infusion-related reactions are excluded if not reoccurring after appropriate pre-medication and/or prolonging infusion time
- Grade 3 non-hematologic laboratory value (excluding lipase, amylase and/or autoimmune endocrinopathies manageable by replacement therapies)
- A delay of  $>2$  weeks due to drug-related toxicity in initiating subsequent cycles, or a second delay lasting  $>24$  h but  $<2$  weeks
- Unable to complete at least 70% of the scheduled treatment, i.e. more than six Debio 1143 skipped doses during any cycle due to treatment-related toxicity or more than 2 treatment interruptions  $>24$  h but  $<6$  days

If for any reason Debio 1143 is withheld temporarily, nivolumab will also be withheld until treatment may be resumed. Patients discontinuing Debio 1143 definitively for any reason will also discontinue nivolumab study treatment.

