Patients requiring no more than 1 treatment interruption per cycle and for not more than 3 consecutive days, may resume treatment without dose adjustments. Patients requiring one interruption greater than 3 days, or more than one interruption during any given cycle, may resume treatment only after full recovery and adjustment of Debio 1143 dose upon the Sponsor's agreement (if applicable).

Patients interrupting treatment or delaying the start of a new cycle due to any Grade 3 treatment-related toxicity will resume treatment after Debio 1143 adjustment (except Grade 3 neutropenia, thrombocytopenia, non-optimally treated fatigue, diarrhea, or nausea). Patients experiencing any Grade 4 treatment-related toxicity will immediately stop treatment without any possible therapy resumption.

Omitted Debio 1143 doses will not be re-administered under any circumstances. Every new cycle D1 will start with the Debio 1143 dose. In case of any cycle delays (Day 1 delayed greater than 72 hours), all

subsequent doses will be administered according to the new planning, if feasible (i.e. Day 1-10 followed by Day 11-14 pause).

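### Protocol Section 5.4 sets two incompatible interruption thresholds for reducing Debio 1143, so two short treatment-related interruptions in Cycle 1 are a DLT under one and not under the other

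*Protocol*

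**What the plan says.** Three places in the Protocol bear on this.

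- **Section 5.4, list of events requiring a reduction.** One bullet names "more than six Debio 1143 skipped doses during any cycle due to treatment-related toxicity or more than 2 treatment interruptions", the interruptions being longer than 24 hours and shorter than 6 days. The text introducing the list reads "Patients experiencing any other treatment-related toxicity fulfilling applicable DLT criteria (as shown below) at any time during the study must stop treatment".
- **Section 5.4, paragraph on resuming treatment.** It opens: "Patients requiring no more than 1 treatment interruption per cycle and for not more than 3 consecutive days, may resume treatment without dose adjustments". By contrast, those with one interruption above 3 days, and those with "more than one interruption during any given cycle, may resume treatment only after full recovery and adjustment of Debio 1143 dose upon the Sponsor's agreement". A bracket limits that agreement to cases where it applies.
- **Section 5.2, DLT definition (also in the synopsis).** More than six skipped doses in Cycle 1 for treatment-related toxicity is a DLT. So is a required reduction in Cycle 1 or on Cycle 2 Day 1 for treatment-related toxicity, even if no other criterion is met.

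Other text in 5.4 narrows the issue. Anyone "interrupting treatment or delaying the start of a new cycle due to any Grade 3 treatment-related toxicity will resume treatment after Debio 1143 adjustment". The bracketed exceptions to this are: "except Grade 3 neutropenia, thrombocytopenia, non-optimally treated fatigue, diarrhea, or nausea". After an interruption on any day but Day 1, if it persists "and the re-treatment criteria are not met within 72 hours, treatment will be resumed only on D1 of the next cycle".

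The SAP adds no interruption threshold. Its Section 18.1.2 takes DLTs from the eCRF flag and has them confirmed at the escalation decision.

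**The concern.** The two parts of 5.4 prescribe the same action at different counts (more than two against more than one) and with different minimum lengths (over 24 hours against none). Neither document says which governs. For dosing alone this would be untidy. It becomes a scoring matter because 5.2 turns a required Cycle 1 reduction into a DLT, and the Part A primary endpoint is the dose selected on DLT counts in 3 to 6 evaluable patients per level. Confirming DLTs at the escalation decision supplies a step, but no single rule to confirm against.

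**Working it through.** **1. The plan's own figure.** Cycle 1 has 20 planned doses (Days 1-10 and 15-24). The 70% evaluability floor is 0.70 × 20 = 14 doses taken, so at most 6 missed, as Protocol Section 6.3 states. Seven missed gives 13/20 = 65%, which fails.

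**2. The rules side by side.** A single missed dose is taken as not exceeding 24 hours (an assumption).

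| Interruptions (doses each) | Missed | Taken | 5.4 list: reduce? | 5.4 resumption paragraph: adjust? | More than six skipped? |
|---|---|---|---|---|---|
| 3 | 3 | 85% | no | no | no |
| 1, 1 | 2 | 90% | no | yes | no |
| 2, 2 | 4 | 80% | no | yes | no |
| 3, 3 | 6 | 70% | no | yes | no |
| 2, 2, 2 | 6 | 70% | yes | yes | no |
| 1, 1, 1 | 3 | 85% | no | yes | no |

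Two interruptions of 1 to 3 doses miss 2 to 6 doses. The patient stays evaluable, the skipped-dose criterion never settles the case, and the two parts of 5.4 disagree.

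**3. Letting the resumption paragraph always govern.** The only patient then resuming without adjustment has one interruption of at most 3 days, hence at most 3 missed doses. Anyone missing 7 or more has already had a second interruption or one above 3 days. Anyone with more than two interruptions has already had more than one. So neither the list's interruption trigger (within a cycle) nor 5.2's more-than-six criterion could ever decide a case.

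The list's trigger could be meant as a count across cycles, since the preceding bullet refers to "weeks due to drug-related toxicity in initiating subsequent cycles, or a second delay lasting" a stated time. The text does not say so, and that reading would not revive the skipped-dose criterion.

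**4. How many patterns are realistic.** Table 5-3 allows dosing on Days 2-10 and 16-24 with Debio 1143-related AEs up to Grade 2, and most Grade 3 events force adjustment anyway. Blood-count limits are the main remaining cause. Cycle 1 hematology after Day 1 is scheduled on Days 8, 15 and 22 (Section 8.2.2.5); Days 3 and 17 cover only liver tests and creatinine. Take starts on those three days, 1 to 3 doses each, with at least one dose taken in between:

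- Days 8 and 15: 2 × 3 = 6 (three doses from Day 8 run up to the pause, leaving none taken before Day 15)
- Days 8 and 22: 3 × 3 = 9
- Days 15 and 22: 3 × 3 = 9
- Total: 24

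If a start were possible on any dosing day after Day 1, with each interruption inside one 10-day block, the count is 975. That ignores the sampling schedule. Both figures describe scope, not frequency.

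**5. A single interruption late in the cycle.** One starting on Day 19, 20 or 21 and not recovered within 72 hours loses 24 − 19 + 1 = 6, 5 or 4 doses: adjustment under the resumption paragraph, none under the list. From Day 18 it loses 7, and the rules agree.

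**6. Effect in 3+3 (Section 5.1.1).** One reclassified patient turns 0/3 into 1/3 (three more patients instead of moving on), or 1/6 = 16.7% into 2/6 = 33.3%. The latter meets the two-or-more rule and fails the requirement of fewer than one-third.

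**The case against.** The strongest reply is that there is one answer. The 5.4 list gives sufficient triggers and does not claim to be complete; it omits some 5.2 criteria, such as Grade 2 cardiac events. The resumption paragraph makes adjustment a condition of restarting, so the reduction is required and the patient is a DLT. This is coherent as a dosing instruction, since a site can follow the stricter rule. It does not settle the scoring. It leaves two written criteria with nothing to decide (step 3), and 5.4 itself presents the list as the applicable DLT criteria.

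Four parts of the reply stand, each against a stronger reading that a reader might infer:

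- **That the Sponsor-agreement wording leaves DLT status open.** It leaves little open. If the Sponsor agrees, the dose is adjusted. If not, 5.4 offers no route to resume, and 5.2 also counts required withdrawal for treatment-related toxicity as a DLT.
- **That the Days 19-21 case matters much.** No hematology is scheduled on those days, and Grade 3 clinical toxicity lasting 3 or more days despite optimal care is already a DLT under 5.2. The case is marginal.
- **That the gap is wide.** The 975 patterns are mostly out of reach for cytopenias found at scheduled tests. A Grade 2 event can explain an interruption only on Day 15, and Table 5-3 exempts several Grade 2 events even then.
- **That the selected dose was affected.** Nothing in the documents shows that any patient fell in this group.

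**Conclusion.** The inconsistency is real and reaches the Part A primary endpoint through the required-reduction criterion in 5.2. It is confined to patients with two short treatment-related interruptions in Cycle 1, 2 to 6 doses missed and no other rule forcing adjustment: 24 patterns at scheduled hematology days, plus any found at unscheduled tests. How often this occurs is unknown, and no rate is assumed here. One such patient is enough to change a 3+3 decision.

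SAP Section 4.3 records futility of the Part B cohorts, so the Part A decision has been made. What can still be gained is a reproducible reported DLT count and consistent dosing for anyone still treated. The conclusion rests on reading an interruption as scheduled doses withheld for treatment-related toxicity, excluding the planned pauses.

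**What to change.** - **Section 5.4:** keep one per-cycle threshold. The resumption paragraph's is the safer one: a second interruption in the cycle, or one of more than 3 days. Say whether a single withheld dose counts as an interruption. Delete the list's trigger of more than two interruptions, or reword it as an explicit count across cycles.
- **Section 5.2:** state whether a reduction triggered only by that interruption rule counts as a DLT.
- **Part A report:** say which rule was applied. For any Cycle 1 patient with two short treatment-related interruptions, give the DLT count under each scoring.

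The cost is a few sentences in the Protocol plus one statement and a short listing in the report. SAP Section 15 already summarises Cycle 1 interruptions and their durations in the RP2D set, so no patients, visits or data are added.

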## 6. STUDY POPULATION

All patients included in the study must have selected advanced/unresectable or metastatic solid tumors, and must have received at least one prior systemic line of standard treatment and have progressed or relapsed during or immediately after a prior anti-PD-1/PD-L1-based treatment, given either as a single agent or in combination with standard/approved chemotherapy, TKIs or other mAbs that are not known to modulate/inhibit immune checkpoints. Patients with prior CTLA-4 or LAG-3 combinations with PD-1/PD-L1 are excluded; any other prior CPI combinations should be discussed and agreed by the Sponsor before patient inclusion.

In Part A:

- Between 3 and 12 evaluable patients are planned.
- Non-evaluable patients will be replaced, as appropriate.

In Part B:

- **Cohort 1:** SCLC (including extrapulmonary small-cell carcinomas or large cell neuroendocrine lung carcinoma, as per WHO Classification of Lung Tumors of 2015 (34))
- **Cohort 2:** SCCHN (nasopharyngeal carcinomas are excluded)
- **Cohort 3:** GI cancers (including esophageal, gastric, colorectal or pancreatobiliary) with known MSI-H/MMRd or other DDR abnormalities, including HRD.
- **Cohort 4:** platinum-resistant EOC, endometrial cancer, PPC or cervical cancer, with known MSI-H/ MMRd, hereditary/somatic mutations of the BRCA1 and BRCA2 genes or other DNA DDR abnormalities (incl. HRD).
- Between 32 evaluable patients (if all cohorts are futile) and 60 evaluable patients (if none of the 4 cohorts is futile) (see [section 11.1](#) for details on sample size).
- Non-evaluable patients will be replaced.

### 6.1. Inclusion criteria

The same tumor types are eligible in Part A and B.

All patients must fulfil all the following criteria (both Parts A and B, unless specified otherwise):

1. Willing and able to sign a written informed consent form;
2. Male or female  $\geq 18$  years of age.
3. Histologically and/or cytologically confirmed advanced/ unresectable or metastatic solid tumor for one the following indications:
  - a. SCLC
  - b. SCCHN (except nasopharyngeal carcinoma)
  - c. GI cancers, including esophageal, gastric, colorectal or pancreatobiliary with known MSI-H/MMRd or any other known DDRs abnormalities, including HRD
  - d. Platinum-resistant\* EOC, endometrial cancer, PPC or cervical cancer, with known MSI-H/ MMRd, hereditary/somatic mutations of the BRCA1 and BRCA2 genes or other known DNA DDRs abnormalities (incl. HRD)  
\* Platinum-resistant is defined as relapse or progressive disease (PD) occurring within 1 to 6 months (180 days) after a platinum-containing chemotherapy.
4. Have received at least one prior line of standard systemic chemotherapy in the advanced/unresectable cancer setting (standard adjuvant/neoadjuvant treatment is acceptable if

- relapse occurred within six months of treatment end) and have no established standard therapeutic alternatives.
5. Have progressed or relapsed during or after a prior anti-programmed cell death-1 (PD-1)/programmed cell death-ligand 1 (PD-L1)-based treatment, given either as a single agent or in combination with standard/approved chemotherapy, tyrosine kinase inhibitors (TKIs), radiotherapy (RT) or other monoclonal antibodies (mAbs) that are not known to modulate/inhibit immune checkpoints (CPIs)
  6. Minimum washout periods since prior therapy until treatment start (C1D1) (in cases of more than one prior treatment type, whichever has the longest minimum period applies):
    - a. 3 weeks for chemotherapy (6 weeks, specifically for nitrosoureas or mitomycin C containing regimens);
    - b. 4 weeks for any prior mAbs or live vaccines; for any investigational mAbs 4 weeks or at least the duration of one treatment cycle whichever is longest
    - c. 3 weeks for prior RT (1 week in case of localized antalgic/hemostatic hypofractionated RT flash)
    - d. 2 weeks for TKIs, hormonal therapy, other anti-cancer treatment not previously specified or investigational agents
    - e. 4 weeks for any major surgery
    - f. Immunosuppressive medication: within 2 weeks, with the exception of intranasal and inhaled corticosteroids or systemic corticosteroids at physiological/replacement doses, which should never exceed 10 mg/d prednisone, or an equivalent corticosteroid
  7. Measurable disease (Part B only) according to RECIST v1.1 or GCIG criteria in Cohort #4 (if applicable) and documented PD during or after prior PD-1/PD-L1 based therapy
  8. ECOG Performance Status = 0 or 1
  9. Adequate hematologic renal and hepatic function:
    - a. absolute neutrophil count (ANC)  $\geq 1.5 \times 10^9/L$ ,
    - b. platelets  $\geq 100 \times 10^9/L$ ,
    - c. hemoglobin  $\geq 9.0$  g/dL,
    - d. AST and ALT  $\leq 3 \times$  ULN ( $\leq 5 \times$  ULN if liver metastases are present),
    - e. total bilirubin  $\leq 1.5 \times$  ULN,
    - f. serum creatinine  $\leq 1.5 \times$  ULN,
    - g. serum albumin  $\geq 30$  g/L
  10. Available archived tumor samples for biomarker analysis obtained after prior PD-1/PD-L1 treatment failure or, if no archived tumor sample is available, patient must be suitable and willing to undergo a percutaneous or endoscopic biopsy without unacceptable major risks before starting study treatment.
  11. Participants with known central nervous system (CNS) and/or meningeal involvement will be eligible if they are clinically asymptomatic, have completed primary CNS therapy more than 4 weeks before treatment start (such as whole brain RT, stereotactic radiosurgery, or complete surgical resection), and have remained off steroids (including tapering doses) for at least 2 weeks
  12. Women of child-bearing potential (WOCBP):
    - a. Negative serum pregnancy test at screening;
    - b. Agreement to use highly effective contraception methods from study entry and for up to 5 months after the last day of study treatment
    - c. Agreement from her male partner to use contraception methods
  13. Male patients with WOCBP partners must agree to use highly effective contraception methods from study entry and for up to 5 months after the last day of study treatment

## 6.2. Exclusion criteria

Any of the following would render a patient ineligible for inclusion (in both Parts A and B, unless specified otherwise):

1. Thoracic or head and neck radiation >30 Gy within the 6 weeks prior to C1D1;
2. Have received, in total, more than 3 (i.e. Cohorts 1&2) or 4 (i.e. Cohorts 3&4) lines of prior systemic treatments (including adjuvant or neoadjuvant regimens if relapse within six months prior to C1D1);
3. Active moderate alcohol consumption, at screening, more than 100/140 grams (3.5/4.9 ounces) of alcohol per week for female and male patients, respectively
4. Liver cirrhosis Child-Pugh score B or C
5. Prior treatment with an anti-CTLA-4 or anti-LAG3 in combination with PD-1/ PD-L1 CPI, unless discussed and agreed with the Sponsor
6. Prior treatment with SMAC mimetics
7. Prior PD-1/PD-L1 discontinuation due to severe immune-related toxicity, not resolved upon adequate steroids/immunosuppressive treatment
8. Requirement of concomitant treatment with any prohibited medication (See [Appendix B: Prohibited medications and special warnings](#))
9. Ongoing toxicity from prior administration of any other investigational drug and/or anti-cancer treatment of > Grade 1 NCI-CTCAE v5.0 before treatment start (except for grade 2 alopecia, stable sensory neuropathy, vitiligo or any endocrinopathy adequately managed by replacement hormonal therapy)
10. Patients with known history of:
  - a. Uncontrolled or symptomatic angina or myocardial infarction, within the last 12 months prior to C1D1
  - b. Elevated (>ULN) troponins (T or I) or creatine phosphokinase (CPK) > 1.5xULN during screening
  - c. Symptomatic intestinal sub-occlusion
  - d. Infection, active or latent by human immunodeficiency virus (HIV), hepatitis B virus (HBV) and hepatitis C virus (HCV)
  - e. Ongoing arrhythmias requiring treatment, including asymptomatic QTc interval as corrected by Fridericia (F) >480 msec
  - f. In patients previously treated with anthracycline-containing chemotherapy or thoracic RT, non-adequate cardiac function with left ventricular ejection fraction (LVEF) <50%, measured by an echocardiogram (ECHO) or a multigated acquisition (MUGA) as per institutional standards
  - g. Active rheumatoid arthritis, active inflammatory bowel disease (IBD), primary sclerosing cholangitis, autoimmune hepatitis, systemic lupus erythematosus (SLE), multiple sclerosis or any other ongoing autoimmune disease requiring systemic treatment (excluding vitiligo, mild cutaneous psoriasis and asymptomatic autoimmune endocrinopathy well controlled under hormonal replacement therapy)
  - h. Evidence of active, non-infectious pneumonitis or a history of interstitial lung disease
  - i. Active ongoing infection requiring systemic antibiotic therapy, including active tuberculosis
11. Evidence or clinical suspicion of active bleeding or requirement of red blood cell (RBC) transfusions within 2 weeks prior to C1D1
12. History of allergic reactions attributed to compounds of similar chemical or biologic composition to Debio 1143 or nivolumab or their constituents
13. History of another non-metastatic, low grade malignancy other than the primary tumor within the last 1 year prior to C1D1, except: completely resected non-melanoma skin cancer, second SCCHN tumors, completely resected minimally invasive bladder cancer, completely resected ≤ pT1N0 invasive breast cancer, low grade prostate cancer if PSA ≤ 10 ng/mL, non-metastatic localized low grade RCC or any previous (non-synchronous) malignancy if related to germ-line mutations linked to either MSI-High-(lynch syndrome) or BRCA-1/2 hereditary cancer syndromes, for patients included either in cohort 3 or 4. For these indications there are no time restrictions with regards to occurrence prior to C1D1.
14. Pregnant or lactating females
15. Unable to swallow or retain oral medications
16. Known contraindication to contrast-enhanced MRI and CT
17. Patient unwilling or unable to comply with study visits/assessments

